6.3.2 Withdrawal from Trial

The patient must be withdrawn from trial in the event of any of the following:

- The patient withdraws consent to participate
- The Investigator judges it necessary due to medical reasons

The EOT and the 1M FUP visits should be performed to the extent possible and the Investigator should ensure any SAE is followed as described in Section [9.3](#).

After the 1M FUP Visit, the Investigator will make every effort to obtain follow-up information on response assessment and/or OS every 2 months. Response assessment follow-up is required in

the event of an ongoing SD, PR or CR, as per RECIST v1.1 at the 1M FUP Visit, until PD or another therapeutic intervention is initiated. Survival follow-up is required until death, withdrawal of consent, or termination of the trial. This continued follow-up does not require an in-person visit at the trial site, but may be obtained by collection of data/documentation.

6.4 Replacement of Patients

6.4.1 Part 1, Dose-Escalation

Patients who do not complete Cycle 1 as defined in Section 9.5.2, for reasons other than drug toxicity, will be replaced.

Data from these patients will be included in the safety analysis, but will not contribute to the determination of the Q2W RP2D.

6.4.2 Part 2

Basket Cohort ONLY: Patients enrolled to the study based on local *MET*-amplification assessments conducted in ctDNA, but with subsequent confirmatory tumor tissue evaluation results not meeting the protocol-specified inclusion criteria, will be replaced (patients may remain on study if there is evidence of an OR, SD, or other clinical benefit, but will not be included in the Evaluable for Response Population).

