Progression from a current dose level to the next will only proceed following evaluation of tolerability of the current dose level. Thus, dosing of the first patient at Dose Level 2 will commence only once all patients to be treated at Dose Level 1 have completed Cycle 1, and Dose Level 1 has been found to be tolerable. Similarly, dosing in Dose Level 3 will only commence once all patients to be treated at Dose Level 2 have completed Cycle 1, and Dose Level 2 has been found to be tolerable. The dose-escalation decision points are listed below:

- If no DLTs are encountered in any of the first 3 patients completing Cycle 1 within a dose level, dose-escalation may continue to the next level
- If 1 of 3 patients within a dose level experiences a DLT, 3 more patients will be enrolled at the same dose level. If no DLTs are encountered in the 3 additional patients, dose-escalation may continue to the next level
- If ≥ 2 patients within a dose level (of up to 6 patients) experience a DLT, then that dose will be considered to have exceeded the MTD and the dose level just below this dose level will be considered to be the MTD
- If no DLTs are encountered in any of the first 3 patients at Dose Level 4, 24 mg/kg will be considered the highest safe dose tested

The SMC will review safety data throughout the trial. During Part 1, the SMC will make decisions regarding the advisability of: continuing accrual to a particular dose cohort; dose-escalation and accrual of patients to a higher dose cohort; and the dose(s) to be used in Part 2 (i.e., Q2W RP2D to be evaluated).

Each patient enrolled will receive Sym015 at the allocated dose until treatment withdrawal, unless dose-reduction is necessary as specified in Section 7.1.4. There will be no intra-patient dose-escalation.

7.1.3.3 Part 2

During Part 2 of this trial, patients will receive the RP2D of Sym015 on a Q2W dosing schedule.

The SMC will continue to review safety data and assess the tolerability of Sym015 during Part 2 of the trial.

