9.5 Dose-Limiting Toxicities (Part 1 Only)

9.5.1 Definition of Dose-Limiting Toxicities

A DLT is defined as any of the following toxicities that occur during the DLT observation period, if considered related (causality rating of possibly, probably, or related) to Sym015:

1. Grade 3 non-hematologic toxicity regardless of duration, with the exceptions of:
 - a. Grade 3 nausea, vomiting, diarrhea, or fatigue lasting \leq 2 days with best supportive care
 - b. Grade 3 asymptomatic electrolyte abnormalities lasting \leq 3 days that are not considered clinically relevant by the Investigator and that resolve with medical therapy
2. Any Grade 4 non-hematologic toxicity, with the exception of:
 - a. Grade 4 asymptomatic electrolyte abnormalities lasting \leq 3 days that are not considered clinically relevant by the Investigator and that resolve with medical therapy.
3. Neutropenia that is:
 - a. Grade 3-4 febrile neutropenia
 - b. Grade 4 and sustained (i.e., ANC <500 per mm³, duration >5 days)
4. Thrombocytopenia that is:
 - a. Grade 3 with clinically significant hemorrhage
 - b. Grade 4 (platelets $<25,000$ per mm³)
5. AST/ALT elevation $>3\times$ ULN with bilirubin elevation $>2\times$ ULN that cannot be explained by factors not related to study drug
6. Inability to complete Cycle 1 at the assigned dose due to \geq Grade 3 toxicity

7. Treatment delays >2 weeks from the scheduled “next dose” due to \geq Grade 3 toxicity

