9.5.2 Observation Period for Dose-Limiting Toxicities

The observation period for DLTs is defined as Cycle 1 with a final assessment 14 (± 2) days after the last dose of Cycle 1 or prior to dosing on C2/D1.

Cycle 1 must have been completed at the assigned dose of Sym015 for a patient to complete the DLT observation period.

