10.3 Analysis Population

Analysis sets will be defined in accordance with the consolidated ICH E9 GCP guidelines.

The Full Analysis Set (FAS) will comprise all enrolled patients who have received at least one dose of Sym015. The FAS will be used for evaluation of all endpoints except evaluation of DLTs. The patients in the FAS will contribute to the analyses as allocated to treatment. For the evaluation of PK endpoints; patients, full profiles, or single measurements can be excluded from the analyses. The decision of excluding patients, full profiles, or part of profiles will be described in the clinical trial report (CTR).

The DLT Analysis Set will comprise all patients in the FAS enrolled in Part 1, except patients who did not complete Cycle 1 (i.e., the initial 28-day period of Q2W dosing) for reasons other than drug toxicity. The DLT Analysis Set will be used for evaluation of DLTs.

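### A Part 1 patient who cannot complete Cycle 1 because of related Grade 1-2 toxicity is a DLT-free member of the Section 10.3 DLT set but falls outside the Section 10.1 DLT-evaluable population

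*Protocol*

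**What the plan says.** Six places in the protocol bear on a Part 1 patient who does not complete Cycle 1 because of drug toxicity.

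- **Section 9.5.1 (DLT definition).** Item 6 is "Inability to complete Cycle 1 at the assigned dose due to" toxicity of Grade 3 or higher. Item 7 covers delays of more than "2 weeks from the scheduled “next dose” due to" toxicity of Grade 3 or higher. Item 5, combined transaminase and bilirubin elevation "that cannot be explained by factors not related to study drug", is the only item that states no grade.
- **Section 6.4.1 (replacement).** "Patients who do not complete Cycle 1 as defined in Section 9.5.2, for reasons other than drug toxicity, will be replaced". No grade is attached to drug toxicity here. The section adds that data from the replaced patients do not contribute to choosing the Q2W RP2D.
- **Section 9.5.2 (observation period).** "Cycle 1 must have been completed at the assigned dose of Sym015 for a patient to complete the DLT observation period".
- **Section 10.1.** Dose-escalation assessment uses a DLT-evaluable population made up of patients who complete the DLT assessment window.
- **Section 10.3.** The DLT Analysis Set, used to evaluate DLTs, is all Part 1 patients in the FAS "except patients who did not complete Cycle 1 (i.e., the initial 28-day period of Q2W dosing) for reasons other than drug toxicity".
- **Section 7.1.3.2 (decision points).** The first bullet reads "If no DLTs are encountered in any of the first 3 patients completing Cycle 1 within a dose level". The bullet on the three expansion patients and the bullet on Dose Level 4 do not mention completing Cycle 1.

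**The concern.** The DLT definition separates patients at Grade 3. The replacement rule and the Section 10.3 analysis set separate them by whether the cause was drug toxicity of any grade. Between these two lines lies the patient who stops early because of a related Grade 1-2 event.

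Under 10.3 that patient enters the primary Part 1 DLT table as a non-event, although 9.5.2 says the observation period was not completed. An incompletely exposed patient is then reported as evidence of tolerability, and the DLT percentage for that dose is pulled down. If the same denominator were used for escalation, a dose would pass on less information than three full Cycle 1 exposures.

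**Working it through.** **1. Planned size.** Four dose levels of three patients give 4 × 3 = 12. One cohort expanded by three gives 12 + 3 = 15. This reproduces the planned 12 to 15. The point does not depend on that figure.

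**2. Classification.** Take a patient who stops after a partial or single dose because of a related Grade 1-2 event that does not meet item 5.

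| Question | Section | Answer |
|---|---|---|
| Is it a DLT? | 9.5.1, items 6-7 | No, the grade is too low |
| Must the patient be replaced? | 6.4.1 | No, the cause is drug toxicity |
| Was the DLT window completed? | 9.5.2 | No |
| In the DLT-evaluable population? | 10.1 with 9.5.2 | No |
| In the DLT Analysis Set? | 10.3 | Yes, without an event |
| Counted for first-step escalation? | 7.1.3.2, first bullet | No, only completers count |
| Counted at expansion or Dose Level 4? | 7.1.3.2, other bullets; 5.2.1 | Not stated |

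Sections 10.1 and 10.3 give opposite answers. Section 10.1 taken literally has the reverse fault as well: a patient whose DLT prevented completion of Cycle 1 would be left out.

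**3. Effect on the DLT percentage.** Suppose an expanded cohort has one DLT, one such non-completer and four completers. Section 10.3 gives 1/6 = 16.7%. Counting only patients who had a DLT or completed Cycle 1 gives 1/5 = 20.0%. With no DLT in the cohort, both percentages are 0 and only the denominator changes.

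**4. Effect on escalation if the 10.3 reading were applied.** Let p be the DLT probability of a fully evaluable patient, which the protocol does not give, and q = 1 - p. Escalation needs 0 DLTs in three, or 1 in three followed by 0 in three more.

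- Three evaluable patients: q³ + 3pq² × q³
- One of the three is such a patient, counted as a non-event and assumed unable to show a DLT: q² + 2pq × q³

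At p = 0.20: 0.512 + 0.384 × 0.512 = 0.709, against 0.64 + 0.32 × 0.512 = 0.804.
At p = 0.30: 0.343 + 0.441 × 0.343 = 0.494, against 0.49 + 0.42 × 0.343 = 0.634.

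| Assumed p | Three completers required | One non-completer counted DLT-free |
|---|---|---|
| 0.10 | 0.906 | 0.941 |
| 0.20 | 0.709 | 0.804 |
| 0.30 | 0.494 | 0.634 |
| 0.40 | 0.309 | 0.464 |

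**5. Without conditioning on such a patient.** Let t be the probability of a low-grade toxicity stop in Cycle 1, also not given. If these patients stay in as non-events, the DLT rate per counted patient is p. If they are left out and others take their place, it is p/(1 - t). At p = 0.20 the first rule gives an escalation probability of 0.709 for any t. The second gives 0.686, 0.660, 0.600 and 0.524 for t = 5%, 10%, 20% and 30%.

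**The case against.** The strongest reply is that escalation does not use the Section 10.3 set. Section 10.1 assigns that decision to patients who complete the window, 9.5.2 defines completion, and the first bullet of 7.1.3.2 counts completers. Section 7.1.3.2 also holds back the next level until all patients to be treated at the current one have completed Cycle 1. A reader might infer that the protocol allows a dose to be cleared on fewer than three full exposures. These texts do not support that for the first step. What remains is that the expansion and Dose Level 4 bullets, and the 0/3 and 1/6 summary in Section 5.2.1, state no completion requirement, and that the reported DLT table follows 10.3.

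A reader might also infer that such a patient may not be replaced. That is not so. Section 6.4.1 merely does not require it, and 7.1.3.2 allows an extra patient so that enough are evaluable.

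A third tempting inference is that the Grade 2 infusion-related reactions in 2 of 3 patients at 18 mg/kg (Section 7.1.3.4) show the problem happening. The protocol does not say that either patient failed to complete Cycle 1. Table 6 places recurrence of symptoms after initial improvement in the Grade 3 row, and 7.1.3.4 treats a Grade 3 reaction as a DLT, so an infusion stopped for such recurrence reads as a DLT. A postponed dose under 7.1.4.2 is a delay and need not mean non-completion. The remaining route is Section 6.3.1, under which the investigator may judge that an AE of any grade requires discontinuation.

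Finally, leaving the patient out of the denominator would also remove a tolerability signal. That is fair, although the SMC reviews safety data throughout and infusion-related reactions of Grade 2 or higher are reported within 24 hours (Section 9.6). It is a reason to list these patients separately.

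**Conclusion.** The concern holds as a contradiction in definitions. The same patient is inside the 10.3 set as a non-event and outside the 10.1 population, is generally not a DLT, and need not be replaced.

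The certain consequence is for the denominator of the Part 1 primary endpoint. The escalation effect is conditional: an increase from 0.71 to 0.80 at a true DLT rate of 20%, and from 0.49 to 0.63 at 30%. It applies only if the 10.3 reading governed the decision, one such patient was among the first three, and that patient could not show a DLT. The DLT rates are assumptions.

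Nothing in the document shows that such a patient occurred. The summary of changes for Amendment 5 (Section 21.5) describes Part 1 as completed, with 12 patients, three per level, and no DLTs. The practical weight therefore lies in how Part 1 is tabulated and reported.

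**What to change.** Reconcile Sections 6.4.1, 7.1.3.2, 9.5.2, 10.1 and 10.3 into one DLT-evaluable definition: Part 1 patients who had a DLT, or who completed Cycle 1 as defined in 9.5.2. The first limb keeps patients whose DLT prevented completion; the second removes incompletely exposed patients without an event. Section 10.3 describes Cycle 1 by elapsed time and 9.5.2 by dose received, so one of these descriptions should serve throughout.

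Use the same term in every decision bullet of 7.1.3.2, make the replacement wording in 6.4.1 consistent with it, and apply it to the Part 1 DLT table. List patients who did not complete Cycle 1 because of toxicity separately, with grade and reason, for the SMC and the clinical trial report. Whether such intolerance should itself be a DLT is for the sponsor and SMC to reconcile.

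The cost is wording in five sections and a check of the Part 1 patients: 12 according to Section 21.5, 12 to 15 as planned.

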7. TREATMENT

7.1 Investigational Medicinal Product/Sym015

The IMP in this trial is Sym015.

Sym015 is a [REDACTED]
[REDACTED]
[REDACTED]
[REDACTED]
[REDACTED]

[figure not shown]
Table 5 Description of Investigational Medicinal Product/Sym015

Ingredients	Quantity per mL	Function
Water	100 mL	Medium
Whey protein	15 g	Medium
Flaxseed oil	10 mL	Medium
Chia seeds	10 g	Medium
Almond milk	100 mL	Medium
Vanilla extract	10 mL	Medium
Maple syrup	10 mL	Medium
Ground flaxseed	10 g	Medium
Ground chia seeds	10 g	Medium
Protein powder	15 g	Medium
Flaxseed oil	10 mL	Medium
Chia seeds	10 g	Medium
Almond milk	100 mL	Medium
Vanilla extract	10 mL	Medium
Maple syrup	10 mL	Medium
Ground flaxseed	10 g	Medium
Ground chia seeds	10 g	Medium
Protein powder	15 g	Medium

Abbreviations (in alphabetical order): q.s., quantum sufficiat (as much as suffices); 6N, normality of 6

1) Acid added for pH adjustment – amount vary from batch to batch

7.1.1 Packaging and Labeling of Sym015

Sym015 will be provided as  Type 1.

Labeling will be in accordance with applicable local regulatory requirements.

7.1.2 Handling, Storage and Preparation of Sym015

All handling, storage, and preparation of IMP should take place at the trial site pharmacy. The Investigator is responsible for informing the pharmacy of the dose of Sym015 to be administered to a given patient, taking into account the patient's body weight.

Sym015 will be [REDACTED] bag prior to administration. The infusion must be completed within 24 hours after preparation of the infusion bag.

A detailed pharmacy guide, specifying handling, storage, and preparation of Sym015, will be provided to the trial sites.

7.1.3 Administration of Sym015

7.1.3.1 Treatment Schedule

All patients will be administered IV infusions of Sym015, dosed according to body weight, through a peripheral line or indwelling catheter, and with the use of an infusion pump and an inline filter. Sym015 will be administered Q2W (Day 1 and Day 15 of each 28-day cycle [± 2 days]).

For all Sym015 infusions, a complete dosing history will be recorded, i.e.,:

- Total dose and volume administered
- Start and stop time of infusion
- Infusion interruption or termination and reason for such actions

7.1.3.2 Part 1, Dose-Escalation

During the dose-escalation part of the trial, the following dose levels of Sym015 administered Q2W will potentially be evaluated in a standard 3+3 dose-escalation design:

- Dose Level 1: 6 mg/kg
- Dose Level 2: 12 mg/kg
- Dose Level 3: 18 mg/kg
- Dose Level 4: 24 mg/kg

A substitute or additional dose level, within the dose levels listed above, could potentially be evaluated. Any decision to add or replace a dose to be tested will be guided by PK data and/or data on target occupancy in skin biopsy samples. This substitute or additional dose level would be chosen between the currently listed dose levels, and a dose higher than 24 mg/kg will not be evaluated without a formal amendment to this protocol.

Cohorts will be filled sequentially until establishment of the highest safe dose. Patients will be allocated to the next available treatment slot within the current or next cohort, as appropriate and depending on the ongoing observation of DLTs and other safety parameters.

Enrollment will be staggered between the first and second patient in each new higher dose level tested. The first patient must have completed and tolerated the first dose of Sym015, including follow-up until Day 8 of Cycle 1 (C1/D8), in order to allow for review of clinical and laboratory assessments. Thereafter patients within a cohort may be added concurrently.

There is potential for entry of additional patients in the dose-escalation portion of the trial to assure a sufficient number of evaluable patients per cohort by entering an additional patient to a cohort (e.g., increase a 3 patient cohort to 4 patients, or a 6 patient cohort to 7 patients).

Note: Should this action be taken, cohort tolerability assessment and subsequent dose-escalation will occur when the minimum number of patients required to evaluate tolerability have completed Cycle 1. However, if any additional patient experiences an event that would, per protocol, result in either cohort expansion or the halting of dose-escalation, protocol rules as outlined herein will be followed.

Progression from a current dose level to the next will only proceed following evaluation of tolerability of the current dose level. Thus, dosing of the first patient at Dose Level 2 will commence only once all patients to be treated at Dose Level 1 have completed Cycle 1, and Dose Level 1 has been found to be tolerable. Similarly, dosing in Dose Level 3 will only commence once all patients to be treated at Dose Level 2 have completed Cycle 1, and Dose Level 2 has been found to be tolerable. The dose-escalation decision points are listed below:

- If no DLTs are encountered in any of the first 3 patients completing Cycle 1 within a dose level, dose-escalation may continue to the next level
- If 1 of 3 patients within a dose level experiences a DLT, 3 more patients will be enrolled at the same dose level. If no DLTs are encountered in the 3 additional patients, dose-escalation may continue to the next level
- If ≥ 2 patients within a dose level (of up to 6 patients) experience a DLT, then that dose will be considered to have exceeded the MTD and the dose level just below this dose level will be considered to be the MTD
- If no DLTs are encountered in any of the first 3 patients at Dose Level 4, 24 mg/kg will be considered the highest safe dose tested

The SMC will review safety data throughout the trial. During Part 1, the SMC will make decisions regarding the advisability of: continuing accrual to a particular dose cohort; dose-escalation and accrual of patients to a higher dose cohort; and the dose(s) to be used in Part 2 (i.e., Q2W RP2D to be evaluated).

Each patient enrolled will receive Sym015 at the allocated dose until treatment withdrawal, unless dose-reduction is necessary as specified in Section 7.1.4. There will be no intra-patient dose-escalation.

7.1.3.3 Part 2

During Part 2 of this trial, patients will receive the RP2D of Sym015 on a Q2W dosing schedule.

The SMC will continue to review safety data and assess the tolerability of Sym015 during Part 2 of the trial.

7.1.3.4 Duration of Infusion for Administration of Sym015

Sym015 will be administered over a 1.5-hour (+10 minutes) period for doses ≥ 18 mg/kg, and over a 1 hour (+10 minutes) period for doses < 18 mg/kg, following delivery of premedication as specified in section [7.2.1](#).

Note: Effective with protocol version 5.0 (November 2016), the duration of infusion has been extended to 1.5 hours for all patients receiving doses ≥ 18 mg/kg due to the occurrence of Grade 2 IRRs in 2 of 3 patients treated in the 18 mg/kg cohort during Part 1 (This action was implemented 13Sep2016).

Administration should be at a constant rate using a programmable volumetric infusion pump in order to assure accuracy of delivery. The times of infusion initiation and completion must be recorded.

The duration of Sym015-infusion will be prolonged for all subsequent patients entered to the trial in the following situations:

- In the event of a Grade 2 IRR in \geq two thirds of the patients entered to a cohort, the duration of infusion for subsequent patients entered at that dose and higher doses will be extended from 1 hour (+10 minutes) to 1.5 hours (+10 minutes) (or longer, if indicated)

Note: This action was implemented 13Sep2016 and applies to doses ≥ 18 mg/kg.

- In the event of a Grade 3 or greater IRR in any patient within a cohort, the duration of infusion for subsequent patients entered at that dose and higher doses will be extended from 1 hour (+10 minutes) to 1.5 hours (+10 minutes) (or longer, if indicated). Such a case will also be considered to have met the protocol criteria for a DLT, thus requiring expansion of the cohort

These same criteria will be applied in the event IRRs occur on the extended 1.5 hours infusion schedule. In such a case, the duration of infusion for subsequent patients entered at that dose and higher doses will be extended to 2 hours (or longer, if indicated).

Recommendations for management of an IRR in individual patients can be found in Section [7.1.3.7](#).

7.1.3.5 Patient Monitoring During and After Infusion of Sym015

Patients will be treated on an outpatient basis.

Sym015 infusions must be administered under the close supervision of an experienced physician in an environment where full resuscitation facilities are immediately available.

Patients will be carefully observed for a minimum of 2 hours following completion of the first administration of Sym015 and a minimum of 1 hour following completion of subsequent administrations. At the end of each infusion, the IV line must remain in place for at least 1 hour to allow administration of IV drugs, if necessary.

